## 10.6. Appendix 6: Liver Safety: Suggested Actions and Follow-up Assessments

### Potential Cases of Drug-Induced Liver Injury

Humans exposed to a drug who show no sign of liver injury (as determined by elevations in transaminases) are termed “tolerators,” while those who show transient liver injury, but adapt are termed “adaptors.” In some participants, transaminase elevations are a harbinger of a more serious potential outcome. These participants fail to adapt and therefore are “susceptible” to progressive and serious liver injury, commonly referred to as DILI. Participants who experience a transaminase elevation above  $3 \times$  ULN should be monitored more frequently to determine if they are an “adaptor” or are “susceptible.”

In the majority of DILI cases, elevations in AST and/or ALT precede TBili elevations ( $>2 \times$  ULN) by several days or weeks. The increase in TBili typically occurs while AST/ALT is/are still elevated above  $3 \times$  ULN (ie, AST/ALT and TBili values will be elevated within the same laboratory sample). In rare instances, by the time TBili elevations are detected, AST/ALT values might have decreased. This occurrence is still regarded as a potential DILI. Therefore, abnormal elevations in either AST OR ALT in addition to TBili that meet the criteria outlined below are considered potential DILI (assessed per Hy’s law criteria) cases and should always be considered important medical events, even before all other possible causes of liver injury have been excluded.

The threshold of laboratory abnormalities for a potential DILI case depends on the participant’s individual baseline values and underlying conditions. Participants who present with the following laboratory abnormalities should be evaluated further as potential DILI (Hy’s law) cases to definitively determine the etiology of the abnormal laboratory values:

- Participants with AST/ALT and TBili baseline values within the normal range who subsequently present with AST OR ALT values  $>3 \times$  ULN AND a TBili value  $>2 \times$  ULN with no evidence of hemolysis and an alkaline phosphatase value  $<2 \times$  ULN or not available.
- For participants with baseline AST **OR** ALT **OR** TBili values above the ULN, the following threshold values are used in the definition mentioned above, as needed, depending on which values are above the ULN at baseline:
  - Preexisting AST or ALT baseline values above the normal range: AST or ALT values  $>2$  times the baseline values AND  $>3 \times$  ULN; or  $>8 \times$  ULN (whichever is smaller).
  - Preexisting values of TBili above the normal range: TBili level increased from baseline value by an amount of at least  $1 \times$  ULN or if the value reaches  $>3 \times$  ULN (whichever is smaller).

Rises in AST/ALT and TBili separated by more than a few weeks should be assessed individually based on clinical judgment; any case where uncertainty remains as to whether it represents a potential Hy's law case should be reviewed with the Sponsor.

The participant should return to the investigator site and be evaluated as soon as possible, preferably within 48 hours from awareness of the abnormal results. This evaluation should include laboratory tests, detailed history, and physical assessment.

In addition to repeating measurements of AST and ALT and TBili for suspected cases of Hy's law, additional laboratory tests should include albumin, CK, direct and indirect bilirubin, GGT, PT/INR, total bile acids, and alkaline phosphatase. Consideration should also be given to drawing a separate tube of clotted blood and an anticoagulated tube of blood for further testing, as needed, for further contemporaneous analyses at the time of the recognized initial abnormalities to determine etiology. A detailed history, including relevant information, such as review of ethanol, acetaminophen/paracetamol (either by itself or as a coformulated product in prescription or over-the-counter medications), recreational drug, supplement (herbal) use and consumption, family history, sexual history, travel history, history of contact with a jaundiced person, surgery, blood transfusion, history of liver or allergic disease, and potential occupational exposure to chemicals, should be collected. Further testing for acute hepatitis A, B, C, D, and E infection and liver imaging (eg, biliary tract) and collection of serum samples for acetaminophen/paracetamol drug and/or protein adduct levels may be warranted.

All cases demonstrated on repeat testing as meeting the laboratory criteria of AST/ALT and TBili elevation defined above should be considered potential DILI (Hy's law) cases if no other reason for the LFT abnormalities has yet been found. **Such potential DILI (Hy's law) cases are to be reported as SAEs, irrespective of availability of all the results of the investigations performed to determine etiology of the LFT abnormalities.**

A potential DILI (Hy's law) case becomes a confirmed case only after all results of reasonable investigations have been received and have excluded an alternative etiology.

## 10.7. Appendix 7: ECG Findings of Potential Clinical Concern

ECG Findings That May Qualify as Adverse Events

 
Marked sinus bradycardia (rate <40 bpm) lasting minutes.
 
New PR interval prolongation >280 msec.
 
New prolongation of QTcF to >480 msec (absolute) or by <math>\geq</math>60 msec from baseline.
 
New-onset atrial flutter or fibrillation, with controlled ventricular response rate: ie, rate <120 bpm.
 
New-onset type I second-degree (Wenckebach) AV block of >30 seconds' duration.
 
Frequent PVCs, triplets, or short intervals (<30 seconds) of consecutive ventricular complexes.
 

ECG Findings That May Qualify as Serious Adverse Events

 
QTcF prolongation >500 msec.
 
New ST-T changes suggestive of myocardial ischemia.
 
New-onset left bundle branch block (QRS >120 msec).
 
New-onset right bundle branch block (QRS >120 msec).
 
Symptomatic bradycardia.
 
Asystole: 
 
In awake, symptom-free patients in sinus rhythm, with documented periods of asystole <math>\geq</math>3.0 seconds or any escape rate <40 bpm, or with an escape rhythm that is below the AV node;
 
In awake, symptom-free patients with atrial fibrillation and bradycardia with 1 or more pauses of at least 5 seconds or longer;
 
Atrial flutter or fibrillation, with rapid ventricular response rate: rapid = rate >120 bpm.
 
 
 
Sustained supraventricular tachycardia (rate >120 bpm) ("sustained" = short duration with relevant symptoms or lasting >1 minute).
 
Ventricular rhythms >30 seconds' duration, including idioventricular rhythm (heart rate <40 bpm), accelerated idioventricular rhythm (HR 40 bpm to
 

<100 bpm), and monomorphic/polymorphic ventricular tachycardia (HR >100 bpm (such as torsades de pointes)).

- Type II second-degree (Mobitz II) AV block.
- Complete (third-degree) heart block.

### **ECG Findings That Qualify as Serious Adverse Events**

- Change in pattern suggestive of new myocardial infarction.
- Sustained ventricular tachyarrhythmias (>30 seconds' duration).
- Second- or third-degree AV block requiring pacemaker placement.
- Asystolic pauses requiring pacemaker placement.
- Atrial flutter or fibrillation with rapid ventricular response requiring cardioversion.
- Ventricular fibrillation/flutter.
- At the discretion of the investigator, any arrhythmia classified as an adverse experience.

The enumerated list of major events of potential clinical concern are recommended as “alerts” or notifications from the core ECG laboratory to the investigator and Pfizer study team, and not to be considered as all inclusive of what to be reported as AEs/SAEs.

## 10.8. Appendix 8: Strong CYP3A Inhibitors and Inducers

This list is not considered as exhaustive. Any questions regarding use of CYP3A inhibitors and inducers should be directed to the Sponsor study team.

[figure not shown]
CYP3A Inhibitors	CYP3A Inducers
HIV antivirals	HIV antivirals
Indinavir	Nevirapine
Nelfinavir	Miscellaneous
Ritonavir	Barbiturates
Saquinavir	Carbamazepine
Boceprevir	Glucocorticoids (systemic)
Lopinavir/ritonavir	Oxcarbazepine
Amprenavir	Phenobarbital
Atazanavir	Phenytoin
Telaprevir	Rifabutin
Darunavir/ritonavir	Rifampin
Fosamprenavir	St. John's wort 
Tipranavir/ritonavir	Troglitazone
Antibiotics	Nafcillin
Clarithromycin	Avasimibe 
Troleandomycin	Enzalutamide
Telithromycin	Mitotane
Anti-infective	
Itraconazole	
Ketoconazole	
Posaconazole	
Voriconazole	
Miscellaneous	
Nefazodone	
Grapefruit juice 	
Conivaptan	
Mibepradiol 	
Idelalisib	

1. The effect of grapefruit juice varies widely among brands and is concentration-, dose-, and preparation-dependent. Studies have shown that it can be classified as a “strong CYP3A inhibitor” when a certain preparation was used (eg, high dose, double strength) or as a “moderate CYP3A inhibitor” when another preparation was used (eg, low dose, single strength).
2. Withdrawn from the United States market.
3. The effect of St. John’s wort varies widely and is preparation-dependent.
4. Not a marketed drug.

[figure not shown]
Reference: U.S. Food and Drug Administration. Drug Development and Drug Interactions: Table of Substrates, Inhibitors and Inducers, available at: <https://www.fda.gov/Drugs/DevelopmentApprovalProcess/DevelopmentResources/DrugInteractionsLabeling/ucm093664.htm>.

## 10.9. Appendix 9: Guidance to Investigators – Management of Individual Participants

[figure not shown]
### Glycemic Control – *including Metformin Dose Starting at Run-In/Visit 2*

## 10.10. Appendix 10: Guidance to Investigators – Management of Individual Participants with Elevation in Fasting Serum Triglycerides

## 10.11. Appendix 11: Guidance to Investigators – Management of Individual Participants With Decrease in Platelet Count

## 10.12. Appendix 12: Abbreviations

The following is a list of abbreviations that may be used in the protocol.

Abbreviation	Term
%CDT	percent carbohydrate deficient transferrin relative to total transferrin
A1AT	Alpha-1-antitrypsin
ABCG2	constitutively expressed ATP-binding cassette transporter
Abs	Absolute
ACC	acetyl-CoA carboxylase
ACCi	acetyl-CoA carboxylase inhibitor (PF-05221304)
AE	adverse event
AESI	adverse event of special interest
ALP	alkaline phosphatase
ALT	alanine aminotransferase
ANCOVA	Analysis of Covariance
Apo	Apolipoprotein
aPTT	activated partial thromboplastin time
AST	aspartate aminotransferase
ATP	adenosine triphosphate
AUC 0-24	area under the concentration-time curve from time 0 to 24 hours
AUC inf	area under the concentration-time curve from time 0 to infinity
AUC tau	area under the concentration-time curve from time 0 to end of dosing period
AUDIT	Alcohol use disorders identification test
AV	Atrioventricular
BBS	Biospecimen Banking System
BCRP	breast cancer resistant protein
BID	bis in die (twice-a-day)
BMI	body mass index
BP	blood pressure
bpm	beats per minute
BUN	blood urea nitrogen
CAP TM	Controlled attenuation parameter
CDT	Carbohydrate deficient transferrin
CFR	code of federal regulations
CI	Confidence Interval
CIOMS	Council for International Organizations of Medical Sciences
CK	creatinine kinase
CK18-M30	cytokeratin-18-M30 fragment
CK18-M65	cytokeratin-18-M65 fragment
CKD-EPI	Chronic Kidney Disease Epidemiology Collaboration equation
C max	peak or maximum observed concentration
CO 2	carbon dioxide (bicarbonate)
CoA	coenzyme A
CONSORT	Consolidated Standards of Reporting Trials
CRF	Case Report Form

Abbreviation	Term
CRO	contract research organization
CSR	clinical study report
CT	clinical trial
$C_{trough}$	plasma concentration before next dose
CYP	Cytochrome P-450 (3A, 2B6, 2C9, 2C19)
D/C	Discontinue
DAG	Diacylglycerol
dB/m	decibels per meter
DCCT	Diabetes Control and Complications Trial
DDI	drug drug interaction
DGAT1	diacylglycerol acyltransferase 1
DGAT2	diacylglycerol acyltransferase 2
DGAT2i	diacylglycerol acyltransferase 2 inhibitor (PF-06865571)
DILI	drug-induced liver injury
DNA	deoxyribonucleic acid
DNL	de novo lipogenesis
DPP-IVi	dipeptidyl peptidase-IV
DU	dispensing Unit
EC	ethics committee
ECG	Electrocardiogram
eCRF	electronic case report form
ED 50	dose that produces half maximum drug effect
EDP	exposure during pregnancy
EFD	embryo-fetal developmental
eGFR	estimated glomerular filtration rate
EMA	European Medical Agency
EU	European Union
EudraCT	European Clinical Trials Database
F/U	follow-up
FFA	free fatty acid
FPG	fasting plasma glucose
FPI	fasting plasma insulin
FSH	follicle-stimulating hormone
GCP	Good Clinical Practice
GGT	gamma-glutamyl transferase
GLP	Good Laboratory Practice
HbA1C	glycated hemoglobin
HBsAg	hepatitis B surface antigen
HCC	hepatocellular carcinoma
HCV RNA	hepatitis C virus genetic material (ie, Ribonucleic acid)
HCVAb	hepatitis C virus antibody
HDL-C	high density lipoprotein cholesterol
HIPPA	Health Insurance Portability and Accountability Act
HIV	human immunodeficiency virus
HOMA-IR	homeostatic model assessment of insulin resistance

Abbreviation	Term
HR	heart rate
HRT	hormone replacement therapy
hs-CRP	high-sensitive C-reactive protein
HSD17b13	17 $\beta$ -Hydroxysteroid dehydrogenase type 13
IB	Investigator's Brochure
ICD	informed consent document
ICH	International Conference on Harmonisation
ID	identification
IND	investigational new drug application
INR	international normalized ratio
IP	investigational product
IPAL	Integrated Path to Architectural Licensure
IRB	Institutional Review Board
IRC	internal review committee
IRT	interactive response technology
IWR	interactive web response
K 2 EDTA	dipotassium ethylenediaminetetraacetic acid
kPa	kilopascals
LDL-C	low density lipoprotein-cholesterol
LFTs	liver function tests
LLN	lower limit of normal
LPLV	last participant last visit
LS	least square
MATE	multidrug and toxin extrusion protein
MCH	mean corpuscular hemoglobin
MCHC	mean corpuscular hemoglobin concentration
MCV	mean corpuscular volume
MedDRA	Medical Dictionary for Regulatory Activities
MELD-Na	model of end-stage liver disease including serum sodium (in addition to serum creatinine, bilirubin, and INR)
MMRM	mixed model repeated measure
MR	magnetic resonance
MRI	magnetic resonance imaging
MRI-PDFF	magnetic resonance imaging using proton density fat fraction acquisition
N/A	not applicable
NAFLD	nonalcoholic fatty liver disease
NASH	Nonalcoholic steatohepatitis
NGSP	National Glycohemoglobin Standardization Program
NOAEL	no observed adverse effect level
non-HDL	non-high density lipoprotein cholesterol
NSAIDs	non-steroidal anti-inflammatory drugs
NTCP	sodium-dependent uptake transporter
NYHA	New York Heart Association
OAT	organic anion transporter (P1B1, P1B3, P2B1)
OATP	organic anion-transporting polypeptide

Abbreviation	Term
OCT2	organic cation transporter 2
PCSK9	proprotein convertase subtilisin/kexin type 9
PD	Pharmacodynamics
PE	physical exam
P-gp	P-glycoprotein
PGx	Pharmacogenomics
PI	principal investigator
PK	Pharmacokinetics
PK/PD	pharmacokinetic-pharmacodynamic
PNPLA3	patatin like phospholipase domain containing protein 3
PreQ	prequalification visit
ProC3	N-terminal propeptide of type III procollagen
ProC6	C-terminal fragment of $\alpha$ 3 chain of procollagen type VI
PT	prothrombin time
PVC	premature ventricular contraction
Q12H	every 12 hours (eg, dosing)
Q8H	every 8 hours
QD	quaque die (once-a-day)
QRS	combination of Q-, R- and S- wave on an electrocardiogram representing ventricular depolarization
QTc	QT interval corrected for heart rate
QTcF	Fridericia's formula, a correction formula for the QC interval
RBC	red blood cell
RNA	ribonucleic acid
RR	interval between 2 successive R waves in a QRS complex
SAE	serious adverse event
SAP	statistical analysis plan
SCR	Screen/Visit 1
SD	standard deviation
SGOT	serum glutamic oxalo-acetic transaminase
SGPT	serum glutamic pyruvic transaminase
SLC10A1	solute carrier Family 10 Member 1
SLCO	solute carrier organic transporter family member (1B1, 1B3, 2B1)
SoA	Schedule of Activities
SOP	standard operating procedure
SREBPs	sterol regulatory-element binding proteins
SRSD	single reference safety document
SSID	service set identifier
SUSAR	suspected unexpected serious adverse reaction
SWE	Sheer wave elastography
$t_{1/2}$	terminal half-life
T1D	type 1 diabetes
T2DM	type 2 diabetes mellitus
TBili	total bilirubin
TEAE	treatment-emergent adverse event

Abbreviation	Term
TI	therapeutic index
TZD	Thiazolidinediones
UDFF™	ultrasound-derived fat fraction
ULN	upper limit of normal
US	United States
VCTE™	Vibration-Controlled Transient Elastography
VLDL	very low-density lipoprotein
WBC	white blood cell
WOCBP	women of childbearing potential

## 1. VERSION HISTORY

**Table 1. Summary of Changes**

Version/ Date	Associated Protocol Amendment	Rationale	Specific Changes
1 / 11-Aug-2020	Original protocol dated 27-Mar-2020 + associated PACL dated 01-Jul-2020	N/A	N/A
2 / 16-Jun-2021	Original protocol dated 27-Mar-2020 + associated PACL dated 01-Jul-2020 + associated PACL dated 22-Jan-2021	Per request from IRC as part of 1 st safety review (May2021) to include derived non-HDL-C	

• Sections 2.1, 3.3.4, 6.3.4, and 7.1.1 were modified to include derived non-HDL-C as endpoint along with summarization, and analysis.

• Appendix 4 was modified to include non-HDL-C acronym definition.

## 2. INTRODUCTION

The current study is to evaluate the effect of coadministration of a range of doses of DGAT2i (ie, PF-06865571) with 1 (and potentially 2) doses of ACCi (ie, PF-05221304), on the primary pharmacology (effect on liver steatosis) and evaluate the ability of a range of doses of DGAT2i to mitigate ACCi-induced elevations in serum triglycerides. This is the first clinical study specifically designed to identify the lowest dose of DGAT2i which, when coadministered with ACCi, results in reduction in hepatic steatosis while mitigating the identified adverse reaction (ie, elevation in serum triglycerides) observed with administration of ACCi alone.

This study has a 2-part design with sequential conduct of Part 1 and Part 2 with each part conducted in distinct/separate cohorts of participants. While the overall study design, objectives/endpoints, eligibility criteria for both parts are envisioned to remain identical, data from Part 1 will be used to determine whether to conduct Part 2. Observed data from Part 1 will guide the selection of doses and dosing regimens (ie, QD vs BID) of DGAT2i + ACCi coadministration evaluated in optional Part 2.

### 2.1. Study Objectives, Endpoints, and Estimands

Objectives	Endpoints	Estimands
Primary:		
To evaluate effect on liver fat, determined by MRI-PDFF, of a range of DGAT2i doses coadministered with a fixed dose of ACCi compared to placebo in participants with presumed NASH.	Percent change from baseline in liver fat as assessed via MRI-PDFF, at Week 6.	Estimand 1
Secondary:		
To evaluate effect on fasting serum triglyceride levels of a range of DGAT2i doses coadministered with a fixed dose of ACCi compared to placebo in participants with presumed NASH.	Percent change from baseline in fasting serum triglyceride levels over time.	Estimand 2
To assess safety and tolerability with a range of DGAT2i doses coadministered with fixed dose of ACCi compared to placebo in participants with presumed NASH.	Proportion of participants with treatment-emergent adverse events (TEAEs) and clinically significant, abnormal clinical laboratory tests, vital signs, and 12-lead ECGs.	Not applicable for safety and tolerability endpoints
Tertiary/Exploratory:		

Objectives	Endpoints	Estimands

To evaluate effect on liver fat determined by quantitative ultrasound (FibroScan®) of a range of DGAT2i doses coadministered with fixed dose of ACCi, compared to placebo in participants with presumed NASH.
	
Percent change from baseline in liver fat at Week 6, as assessed by CAP™ via FibroScan®.
	Estimand 1

To evaluate effect on liver function tests of a range of DGAT2i doses coadministered with fixed dose of ACCi, compared to placebo in participants with presumed NASH
	
 
Percent change from baseline, over time, in:           
 
ALT
 
AST
 
Alkaline Phosphatase
 
Total Bilirubin and
 
GGT
 
 
 
	Estimand 2

To evaluate effect on metabolic parameters of a range of DGAT2i doses coadministered with fixed dose of ACCi, compared to placebo in participants with presumed NASH
	
 
Percent change from baseline, over time, in:           
 
Total cholesterol
 
Direct LDL
 
HDL-C
 
Direct VLDL
 
Apolipoprotein A1, Btotal, B100, B48, C3, and E
 
Derived non-HDL-C
 
 
 
Change from baseline, overtime, in:           
 
HbA1C
 
FPG
 
FPI
 
HOMA-IR
 
 
 
	Estimand 2 Estimand 3

To evaluate the effect on mechanism/disease-related biomarkers of a range of DGAT2i doses coadministered with fixed dose of ACCi, compared to placebo in participants with presumed NASH
	
 
Percent change over time in:           
 
CK 18-M30, -M65
 
Pro-C3, and Pro-C6
 
PCSK9
 
Adiponectin
 
hsCRP
 
 
 
	Estimand 2

To summarize plasma PK of DGAT2i and ACCi, across the active doses of DGAT2i + ACCi evaluated in participants with presumed NASH
	
Predose DGAT2i and ACCi plasma concentrations (ie, Cthrough)
	Not Applicable for this analysis

To enable the exploratory research through collection of banked biospecimens, unless prohibited by local regulations or ethics committee decision
	
Biobanking of blood-based specimens (including Prep D1, B1.5, and B2.5 collections to permit retrospective analysis of yet-to-be identified biomarkers)
 
 
These results may or may not be generated in the context of the present study
 
	Not Applicable for this analysis

### 2.1.1. Estimand 1

For a given endpoint, the estimand will be the estimated population based average treatment effect on ***natural log-transformed relative change*** from baseline for DGAT2i + ACCi relative to placebo ***at Week 6*** for all randomized/evaluable participants.

#### Intercurrent Events:

- Non evaluable baseline – All data collected post-randomization will be excluded.
- Withdrawal from study intervention after randomization – All data collected after a participant stops taking study intervention will be excluded.
- Prohibited medications – All assessments after a participant receives prohibited medications that would modulate the primary endpoint will be omitted from the analysis. The list of concomitant medications would be reviewed prior to database lock to determine which would be classed as “prohibited” for this estimand.
- Inadequate compliance – All randomized/evaluable participants with compliance <80%, over the ***entire duration of dosing*** with double-blind, double-dummy study intervention, will **not** have their endpoint measurement used as recorded in the analysis.

#### Population level summary:

- The population level summary will be the mean difference in natural log-transformed relative change from baseline between DGAT2i + ACCi groups and placebo groups for the endpoint of interest at Week 6.

### 2.1.2. Estimand 2

For a given endpoint, the estimand will be the estimated population based average treatment effect on ***natural log-transformed relative change*** from baseline for DGAT2i + ACCi relative to placebo ***over time*** for all randomized/evaluable participants.

#### Intercurrent Events:

- Non evaluable baseline – All data collected post-randomization will be excluded.
- Withdrawal from study intervention after randomization – All data collected after a participant stops taking study intervention will be included.
- Prohibited medications – All assessments after a participant receives prohibited medications that would modulate the endpoint will be omitted from the analysis. The list of concomitant medications would be reviewed prior to database lock to determine which would be classed as “prohibited” for this estimand.

- Inadequate compliance – All randomized/evaluable participants, *regardless of the level of compliance*, will have their endpoint measurement used as recorded in the analysis.

Population level summary:

- The population level summary will be the mean difference in natural log-transformed relative change from baseline between DGAT2i + ACCi groups and placebo groups for the endpoint of interest *over time*.

### 2.1.3. Estimand 3

For a given endpoint, the estimand will be the estimated population based average treatment effect on ***change from baseline*** for DGAT2i + ACCi relative to placebo ***over time*** for all randomized/evaluable participants.

Intercurrent Events:

- Same as Estimand 2.

[figure not shown]
Population level summary:

- Same as Estimand 2 but with the mean difference in change from baseline between DGAT2i + ACCi groups and placebo groups for the endpoint of interest *over time*.

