Given DGAT2i is a dose-dependent inhibitor of the transporters OCT2/MATE in kidney, as expected, increases in serum creatinine without a change in renal function (as assessed via eGFR determined using Cystatin-C) was noted. Dosing with ACCi alone resulted in 2 identified adverse drug reactions – namely, increases in fasting serum triglycerides, and decrease in platelet count, with reversal in 1 to 2 weeks post discontinuation of ACCi alone observed, refer to [Section 2.3.1](#). Based on review of pooled TEAEs, 12-lead ECG data, blood pressure data, and laboratory data, coadministration of DGAT2i + ACCi has been shown to not result in worsening of the safety profile relative to either agent administered alone. However, coadministration of DGAT2i + ACCi at the doses tested in Study C3711001 (300 mg BID + 15 mg BID) was shown to mitigate the ACCi-induced elevations in fasting serum triglycerides, ApoC3, and non-HDL. There were no clinically significant adverse effects noted in other safety-related assessments such as blood pressure, and cardiac conduction intervals [assessed on 12-lead ECGs] with DGAT2i, ACCi, and DGAT2i + ACCi.

Upon repeated dosing of DGAT2i with standard meals,  $C_{max}$  was achieved at 1.5-3 hours post dose. Steady-state plasma concentrations were achieved by Day 4, and the mean terminal  $t_{1/2}$  ranged from 3.3-6.9 hours. Dosing in the fasted state resulted in lower exposures (ie,  $AUC_{inf}$  39% lower and  $C_{max}$  34% lower than when a 1000 mg DGAT2i dose was administered with a standard meal). Following oral dosing of ACCi with a high-fat/high-caloric meal,  $C_{max}$  was achieved at 3-5 hours post-dose, and the mean terminal  $t_{1/2}$  ranged from 13-18 hours. There was no clinically relevant effect on exposure with dosing of ACCi in the fasted versus fed state. Coadministration of DGAT2i (300 mg BID) and ACCi (15 mg BID) resulted in a slight decrease in the systemic exposure of ACCi with adjusted geometric mean (90% CI) of 12% (2-20%) lower (for  $C_{max}$ ) and 19% (12-26%) lower (for  $AUC_{tau}$ ). There was no marked effect on the systemic exposure of DGAT2i, when coadministered with ACCi, with adjusted geometric mean 8% higher (for  $C_{max}$  and  $AUC_{tau}$ ).

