### 8.2.5. Clinical Safety Laboratory Assessments

See [Appendix 10.2](#) for the list of clinical safety laboratory tests to be performed and SoA - [Table 2](#) for the timing and frequency. All protocol-required laboratory assessments, as defined in [Appendix 10.2](#), must be conducted in accordance with the laboratory manual and SoA - [Table 2](#). Unscheduled clinical laboratory measurements may be obtained at any time during the study to assess any perceived safety issues.

The investigator must review the laboratory report, document this review, and record any clinically relevant changes occurring during the study in the AE section of the CRF.

Clinically significant abnormal laboratory findings are those which are not associated with the underlying disease, unless judged by the investigator to be more severe than expected for the participant's condition.

All laboratory tests with values considered clinically significantly abnormal during participation in the study or within ***28 days after the last dose of study intervention*** should be repeated until the values return to normal or baseline or are no longer considered clinically significant by the investigator or medical monitor.

If such values do not return to normal/baseline within a period of time judged reasonable by the investigator, the etiology should be identified, and the Sponsor notified.

See [Appendix 10.6](#) for suggested actions and follow-up assessments in the event of potential drug-induced liver injury.

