### 8.2.8. Triggered Requirements and Individual Participant Stopping Rules

#### 8.2.8.1. Potential Cases of Hypertriglyceridemia

In the current study, fasting serum triglycerides as reported by the Sponsor-identified central laboratory, with or without any accompanying signs/symptoms, will be assessed versus the threshold outlined in [Appendix 10.10](#).

Individual participants with consistently increasing ***fasting*** serum triglycerides ***over time (or*** double-confirmed result) ultimately reaching the threshold of  $\geq 800$  mg/dL ( $\geq 9$  mmol/L) as outlined in [Appendix 10.10](#) should stop dosing with study intervention and an AE of hypertriglyceridemia captured.

**NOTE:** dose(s) of background agent(s) for lipid control (refer to [Section 6.5.2](#)) must ***not*** be adjusted while in this study as it compromises ability to evaluate effectiveness of DGAT2i + ACCi to mitigate ACCi-induced elevations in serum triglycerides.

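### Estimand 2 counts triglycerides drawn after study drug is stopped, although high triglycerides are themselves a reason to stop; any such values reaching the treatment visits understate the rise, most in the least-mitigated arms

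*SAP*

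**What the plan says.** SAP 2.1.2 and Protocol 9.1.1 give Estimand 2 a treatment-policy rule for stopping drug: "Withdrawal from study intervention after randomization – All data collected after a participant stops taking study intervention will be included". SAP 6.2.1 applies this estimand to fasting triglycerides. Estimand 1, used for liver fat, has the opposite rule (SAP 2.1.1): "All data collected after a participant stops taking study intervention will be excluded".

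Under Protocol 8.2.8.1, participants whose fasting triglycerides climb to 800 mg/dL or more, over time or on a confirmed result, "should stop dosing with study intervention and an AE of hypertriglyceridemia captured". The same section forbids changes to background lipid drugs "as it compromises ability to evaluate effectiveness of DGAT2i + ACCi to mitigate ACCi-induced elevations in serum triglycerides". Protocol 2.2.1 describes the two identified ACCi reactions as "increases in fasting serum triglycerides, and decrease in platelet count, with reversal in 1 to 2 weeks post discontinuation of ACCi alone observed".

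The triglyceride MMRM covers Weeks 2, 4, 6 and Follow-Up (Protocol 9.4.2). Protocol 4.1.2 lists the degree of triglyceride mitigation among the data reviewed after Part 1 to guide Part 2.

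**The concern.** The endpoint triggers the intercurrent event, and the event removes the cause of the rise. A participant in an arm with too little DGAT2i can reach the threshold, stop, and return toward baseline. Under Estimand 2 that reversed value counts for the assigned arm like an on-drug value. It then reflects the absence of ACCi, not mitigation by DGAT2i.

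Stops for high triglycerides should be most frequent where mitigation is weakest, so the distortion favours the lowest DGAT2i doses. The study seeks the lowest dose that mitigates, so this is the direction that matters. The protocol already protects the comparison from changes in lipid drugs, but nothing in the analysis does the same for stopping ACCi. SAP Appendix 2.1 defines an on-treatment assessment, yet no triglyceride analysis uses it.

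**Working it through.** **The plan's own figure.** The only power statement is for liver fat (Protocol 9.2.1). It reproduces: |ln 0.75| = 0.288; standard error 0.221 × √(2/15) = 0.0807; 0.288/0.0807 − 1.645 = 1.92, a power of 97%, which agrees with the stated figure of more than 90%. No figure is given for triglycerides, so the size below rests on assumptions.

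**Can off-drug values reach the model?**
- Protocol 7.1 and 7.2: a participant who definitively discontinues drug leaves the study. Protocol 7.2.1: those who ask to stop drug remain and are followed. These conflict.
- Protocol 8.2.5: clinically significant results "should be repeated until the values return to normal or baseline or are no longer considered clinically significant". The Study D/C visit also includes triglycerides (Schedule of Activities, Table 2).
- SAP Appendix 2.1: the Day 36–48 window requires assessments within 72 hours of last dose. The table rows look displaced in the extracted text; the limit is read as Week 6 because that window is centred on Day 42. The Day 22–34 window (Week 4) has no such limit, and windowing applies to SAP 6.2.1.
- SAP 3.5.2 frames laboratory inclusion around scheduled visits, and early withdrawals keep a nominal visit label. Both may keep unplanned rechecks out, but neither says so.

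Week 4 is therefore the visit most exposed: a recheck 1 to 2 weeks after a stop at Week 2 falls in its window.

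**Arithmetic for one arm of 18.** Suppose *k* participants would have stayed at 800 mg/dL on drug and instead return to baseline *b*. The arm's geometric mean ratio at a visit where those values count is multiplied by (*b*/800)^(*k*/18). Take *b* from 400 mg/dL (the eligibility ceiling) down to 150 mg/dL (assumed). As a yardstick use +28%, the upper 90% confidence limit that Protocol 4.3.1 cites from Study C3711001.

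| Stoppers of 18 | Multiplier | A true +28% appears as |
|---|---|---|
| 1 | 0.96 to 0.91 | +23% to +17% |
| 2 | 0.93 to 0.83 | +19% to +6% |
| 3 | 0.89 to 0.76 | +14% to −3% |

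**How many stop?** The documents do not say. The nearest figure is the 6% rate of hypertriglyceridemia events on ACCi alone at 2–200 mg/day (Protocol 2.2.1). That is a loose proxy: it is not limited to values of 800 mg/dL or more, and no DGAT2i was given. It implies 18 × 0.06 = 1.08 per arm, with P(at least 1) = 1 − 0.94^18 = 67%, P(at least 2) = 29% and P(at least 3) = 9%.

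**Simulation at Week 4.** None of these inputs is in the documents: on-drug log-ratio SD 0.5; within-person correlation 0.7; median baseline 200–260 mg/dL with log SD 0.4, truncated at 400; a stop at any visit value of 800 mg/dL or more; off-drug log-ratio centred at zero with SD 0.25; every stopper sampled afterwards.

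| Mean log-ratio | True rise | Stopping by Week 4, of 18 | Week 4 estimate, off-drug values included |
|---|---|---|---|
| 0.35 | 42% | about 1–2 | 33–36% |
| 0.50 | 65% | about 2–3 | 48–54% |

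Only stops at Week 2 affect the Week 4 mean. If the 72-hour limit blocks off-drug Week 6 values, Week 6 in the first case still falls to about 38–40%, because the model predicts the missing values from reversed Week 4 values. Setting off-drug values to missing and fitting by likelihood recovered the true rise.

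**The case against.** The strongest reply is that the data may largely not exist. A participant stopped under the threshold rule leaves the study under Protocol 7.1 and 7.2. The contrary text in 7.2.1 sits under withdrawal of consent and speaks of participants who ask to stop. The discontinuation sample, taken soon after the decision, may still be high. Week 6 is protected by the 72-hour limit, and unplanned rechecks may not qualify under SAP 3.5.2. Protocol Appendix 10.10, which governs management after the threshold, is a figure not shown in the public text. This stands as a limit on size. It does not close the Week 4 route, because none of these passages excludes such values and Estimand 2 expressly admits them.

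Stops also remain visible: 800 mg/dL is an event of special interest (Protocol 8.3.6) and an alert level counted by participant (SAP 3.5.2). No formal test or decision rule rests on the MMRM, and PK/PD modelling also informs Part 2. This is true, but counts beside a mean do not correct the mean.

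A reader might infer that an inadequate dose would appear to mitigate. The figures do not support that: the simulated arms still show +33% or more at Week 4, and in the arithmetic +28% disappears only with three of 18 stopping from a low baseline and reversing fully. A reader might also take Week 6 as the worst-affected visit. Carrying off-drug values forward there gives larger distortions, but the 72-hour limit excludes them. Nor is Estimand 2 wrong in itself: treatment policy is a legitimate strategy, but it does not answer the on-drug question alone.

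**Conclusion.** The point holds as a conditional bias in a known direction. Where off-drug triglycerides enter the treatment visits, the estimated rise is too small, most in the arms that mitigate least. Under the stated assumptions the loss at Week 4 is about 6 to 9 percentage points from a true 42%, and about 11 to 17 points from a true 65%. With few stoppers, or none sampled after stopping, it is small. The result is attenuation, not apparent full mitigation.

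The direction rests on the stopping rule, the reported reversal and Estimand 2's inclusion rule. The size rests on inputs the documents do not give: the stopping rate, the triglyceride variability and how much sampling follows a stop. The documents do not support making an on-treatment estimate the only basis for dose choice. This is a cheap improvement to the plan, not a flaw that invalidates it.

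**What to change.** 1. Keep Estimand 2. Add to SAP 2.1 and 6.2.1 a supplementary on-treatment estimand for fasting triglycerides: the same MMRM at Weeks 2, 4 and 6, with values after last dose set to missing. State how that cut-off relates to the 72-hour allowance, so that end-of-treatment samples are handled as intended.
2. At the post-Part 1 review, show it beside the Estimand 2 result and the number per arm who stopped for triglycerides. Read Follow-up as an off-drug summary of reversibility.
3. Reconcile Protocol 7.1 and 7.2 with 7.2.1, and Estimand 2's inclusion of all post-stop data with the 72-hour limit on Week 6. State whether unplanned rechecks can fill a visit window. Which follow-up rule is right is for the sponsor to settle; the stopping rule is not in question here.

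The cost is SAP wording and one extra model on data already collected. The downside is reliance on missing at random. That is plausible where the scheduled value that led to the stop stays in the model, and less so where the decision turned on an unplanned confirmatory sample outside it.
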